This is a randomized, placebo-controlled dose escalation study that will evaluate the safety and efficacy of 3 tildacerfont dose levels (50 mg, 100 mg, and 200 mg QD) compared to placebo for up to 12 weeks of treatment in subjects with PCOS and elevated adrenal androgens at baseline. The study is planned as a 3-period study with a duration of 4 weeks for each period.	
The Schedule of Activities is provided in Section 12.2 .	

Subjects diagnosed with PCOS per the 1990 NIH criteria ([Zawadski and Dunaif, 1992](#)) will be screened to determine eligibility for the study over up to 2 screening visits. For subjects with unknown DHEAS elevations (within 6 months of target randomization date), an optional DHEAS Screening Visit may be used to test DHEAS level prior to further screening evaluations. In order to qualify for the study, a subject's DHEAS value must exceed the age-matched, reference ULN threshold. Screening Visit assessments will include safety laboratories and assessments. Subjects meeting all eligibility criteria will be randomized to either dose escalation with tildacerfont or matching placebo.

Subjects randomized to the tildacerfont group will initiate treatment with 4 weeks of 50 mg QD, then proceed to 4 weeks at 100 mg QD and complete the study with 4 weeks at 200 mg QD. All placebo subjects will remain on placebo over the full 12-week treatment period.

If signs, symptoms or biochemical evidence of adrenal insufficiency are noted, study drug will be suspended until adrenal function may be fully evaluated for relationship to clinical findings. If adrenal insufficiency is confirmed, study drug will be permanently discontinued.

Study drug will be administered at home during each period with an evening meal that should contain approximately <50% fat content.

Efficacy Assessments

Blood samples will be collected at every clinic visit for measurement of serum DHEAS levels.

Safety Assessments

Safety assessments will include monitoring and recording all AEs (including SAEs, AEs leading to discontinuation/withdrawal, and AESIs), physical examination, vital signs assessment, ECGs, clinical laboratories, including serum cortisol, and monitoring for suicide risk using the Columbia-Suicide Severity Rating Scale (C-SSRS).

PK Assessments

PK assessments will be conducted at Weeks 4, 8, and 12 and will consist of a single sample at 8 A.M. (\pm 1 hour).

Study Conduct:

Each subject's course will consist of the following visits:

Clinic Visits

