Clinic visits will occur at the following times:

- Optional DHEAS Screening Visit
- Screening Visit (Safety labs and assessments, inclusion/exclusion criteria evaluation, medical history, and concomitant medications)
- Treatment Period:
 - Period 1: At Day 1 and Day 28
 - Period 2: Day 56
 - Period 3: Day 84
- Follow-up: At 30 days after the last dose of study drug

Clinic visits should be scheduled for the early morning, to accommodate morning laboratory assessments (approximately 8 A.M. \pm 1 hour). DHEAS is expected to peak in the morning after overnight ACTH surge, so morning draws are optimal for the DHEAS Screening Visit. However, any previously documented DHEAS elevation will confirm eligibility during the optional pre-screening visit.

Telephone Contacts

Sites will make scheduled telephone contacts to all subjects at Weeks 2, 6, and 10 to assess for the occurrence of AEs and the initiation of new concomitant medications.
 
Subjects should be instructed to telephone sites if they have any concerns about their health and/or to report AEs.

Duration of Subject Participation: Approximately 25 weeks, inclusive of up to 30 days of optional DHEAS screening, 30 days of screening, 12 weeks of treatment, and 30 day follow up.

Planned Sample Size and Number of Sites: This study will enroll approximately 40 subjects at approximately 15 investigative sites within North America.

Study Drug and Route of Administration: Tildacerfont, an oral small-molecule corticotropin-releasing factor type-1 (CRF₁) receptor antagonist will be supplied as 50 mg tablets. Placebo will be supplied as tablets that look identical to drug product but contain no drug substance.

Subject Population: Female subjects 18 to 40 years old with PCOS and screening DHEAS levels that exceed the age-matched reference ULN threshold.

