1.2. Study Rationale

1.2.1. Rationale for the Study Design

The SPR001-210 study is a randomized, placebo-controlled, dose escalation study that will evaluate the preliminary efficacy and safety of tildacerfont (50 mg, 100 mg, and 200 mg once daily [QD]) compared to placebo after 12 weeks of double-blind treatment in subjects with PCOS and elevated adrenal androgens at baseline. Subjects randomized to the tildacerfont group will receive 3 escalating dose levels of tildacerfont with each dose level administered for 4 weeks. All subjects randomized to placebo will remain on placebo over the full 12-week treatment period. To be able to characterize changes and the magnitude of changes in DHEAS as due to treatment and to account for any inherent variability in DHEAS, a placebo treatment group is warranted. Four weeks of treatment was deemed minimally adequate to observe change in hormones and androgens, given the exposure profile of tildacerfont which achieves steady state after approximately 2 weeks of dosing.

DHEAS is the primary hormone being evaluated in this study and was selected as a stable biomarker of androgen production. Additionally, reduction in DHEAS was chosen as the efficacy endpoint as the vast majority (>90%) of DHEAS is produced in the adrenal glands and is therefore representative of an adrenal source of hyperandrogenemia, which is the population that may potentially be addressed with tildacerfont. The level of receptor occupancy necessary to result in reduction in DHEAS in subjects with PCOS is unknown. A dose of 50 mg is expected to result in ≤50% receptor occupancy while a dose of 200 mg is expected to provide ≥90% receptor occupancy. The range of doses was chosen to understand if increasing dose can provide additional reductions in DHEAS levels.

Additionally, the study will provide preliminary safety data over up to 12 weeks of treatment with tildacerfont in the PCOS population. Safety visits are planned every 4 weeks at the end of each treatment period at a dose level with a scheduled telephone call 2 weeks after initiating each tildacerfont dose level. The level of safety monitoring should provide adequate oversight

given the observed safety and tolerability profile to date. The study population will include women (18 to 40 years of age) with PCOS, characterized by the presence of hyperandrogenemia as indicated by a screening serum DHEAS level > age-matched reference ULN.

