3.1.1. Dose Escalation

Subjects randomized to the tildacerfont group will initiate treatment with 4 weeks of 50 mg QD, then proceed to 4 weeks at 100 mg QD and complete the study with 4 weeks at 200 mg QD. All placebo subjects will remain on placebo over the full 12-week treatment period. If signs, symptoms or biochemical evidence of adrenal insufficiency are noted, study drug will be suspended until adrenal function may be fully evaluated for relationship to clinical findings. If adrenal insufficiency is confirmed, study drug will be permanently discontinued and treatment will be managed by the Investigator according to standard medical practice. Complete stopping criteria for adrenal insufficiency are provided in [Section 6.1.6](#).

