ALT \geq 3x ULN	
Treatment Periods 1 and 2:
 
 
Monitor liver chemistry (AST/ALT/ALP), total bilirubin, total bile acids, CBC with differential and INR within 48-72 hours and notify Sponsor 
If no other stopping criteria are met, monitor AST/ALT/ALP and INR 2x weekly for the remainder of the current treatment period (may be performed weekly if AST/ALT stabilizes and the subject is asymptomatic) while continuing study drug 
If ALT $>3x$ ULN at the conclusion of the current treatment period, withdraw the subject from the study 
Treatment Period 3:
 
 
Follow the same notification and monitoring instructions detailed in (a) and (b) above for Treatment Periods 1 and 2. 
If ALT $>3x$ ULN persists for 4 weeks, discontinue study drug and notify Sponsor

Criteria	Actions	
ALT \geq 3x ULN	AND total bilirubin \geq 2x ULN (>35% direct bilirubin) ¹	Discontinue study drug and notify Sponsor. Possible Hy's Law case— report as SAE and AESI
	AND INR >1.5	Discontinue study drug and notify Sponsor. Possible Hy's Law case— report as SAE and AESI
	AND total bile acids $>3x$ ULN	Hold study drug and notify Sponsor. Measure liver chemistry (AST/ALT/ALP), total bilirubin, total bile acids, CBC with differential and INR within 48-72 hours and discuss with Medical Monitor whether to discontinue study drug.
	AND the appearance of fatigue, nausea, vomiting right upper quadrant pain or tenderness, jaundice, fever, rash and/or eosinophilia (>5%).	Discontinue study drug and notify Sponsor.

Abbreviations: AESI, adverse event of special interest; ALP, alkaline phosphatase; ALT, alanine aminotransferase; AST, aspartate aminotransferase; CBC, complete blood count; INR, international normalized ratio; SAE, serious adverse event; ULN, upper limit of normal.

¹ If serum bilirubin fractionation is not immediately available, discontinue study drug if ALT \geq 3x ULN and bilirubin \geq 2x ULN and record the presence/absence of detectable urinary bilirubin on dipstick, which is indicative of direct bilirubin elevations suggesting liver injury.

Investigation of the underlying cause of these transaminase elevations should include, but is not limited to:

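### The Treatment Period 3 item for isolated ALT >3x ULN needs 4 weeks of persistence inside the final 4-week period, so on the nominal schedule it cannot stop dosing

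*Protocol*

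**What the plan says.** Table 2 in Protocol Section 6.1.2 treats a raised ALT with no other criterion differently by period.

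- **Periods 1 and 2.** The subject is retested and then monitored for the rest of the period. Testing may become less frequent if the transaminases settle: "stabilizes and the subject is asymptomatic) while continuing study drug". If ALT is above 3x ULN when the current period ends, the instruction is to act at the end of that "treatment period, withdraw the subject from the study". No minimum duration is attached.
- **Period 3.** The same notification and monitoring apply, but dosing stops only if ALT above 3x ULN "persists for 4 weeks, discontinue study drug and notify Sponsor".

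The Synopsis fixes the calendar: "The study is planned as a 3-period study with a duration of 4 weeks for each period". The clinic visits that close the last two periods are "Period 2: Day 56" and "Period 3: Day 84". Section 3.1.1 makes Period 3 the last stretch of treatment, in which subjects "complete the study with 4 weeks at 200 mg QD".

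**The concern.** The persistence condition is as long as the period it applies to, and that period is the last one. An elevation that arises on 200 mg can complete 4 weeks only when there is no dosing left to stop. Nor can the clock properly start in Period 2, because the end-of-period rule removes a subject who is still above 3x ULN at that point.

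At stake is whether a line presented as a stopping criterion can do anything while subjects receive the highest dose level. A site or ethics board reading Table 2 would take it to be a working rule. Protocol Section 1.3 lists hepatotoxicity among the potential risks from non-clinical work, so the table should mean what it says.

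**Working it through.** **Inputs**

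- Period 3 runs from the Day 56 visit to the Day 84 visit (Synopsis, clinic visits).
- The persistence needed is 4 weeks, or 28 days (Table 2).
- Dosing is with the evening meal (Section 5.1) and laboratory draws are at about 8 A.M. (Section 7.1.5). The Day 56 draw therefore precedes the first 200 mg dose, and the earliest draw after such a dose is the morning of Day 57. That draw would be unscheduled.
- Drug for Period 3 is dispensed at Week 8 (Section 3.1.2.4) and returned at Week 12 (Section 5.5). The last evening dose is thus nominally Day 83. Day 84 is the generous variant.
- Visit windows are ±1 day (Section 12.2, footnote 1). The SAP's target study days for the same two visits are 57 and 85 (SAP Section 9.4).

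**Check of the plan's own figure.** Day 84 − Day 56 = 28 days = 4 weeks, as stated. Period length minus required persistence = 28 − 28 = 0 days of margin.

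**Formulas**

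- Day the condition is met = day of first ALT >3x ULN + 28.
- Doses avoided = max(0, last dose day − day met + 1).

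Figures in brackets assume that a dose is still taken on the evening of the Week 12 visit.

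| Case | First ALT >3x ULN | Condition met | Last dose | Doses avoided |
|---|---|---|---|---|
| Nominal, earliest draw after 200 mg | Day 57 | Day 85 | Day 83 (84) | 0 (0) |
| Nominal, one day later | Day 58 | Day 86 | Day 83 (84) | 0 (0) |
| Nominal, scheduled Week 12 draw | Day 84 | Day 112 | Day 83 (84) | 0 (0) |
| SAP target days 57 and 85, earliest draw | Day 58 | Day 86 | Day 84 (85) | 0 (0) |
| Week 8 visit on Day 55, Week 12 visit on Day 85, unscheduled draw the morning after the first 200 mg dose | Day 56 | Day 84 | Day 84 (85) | 1 (2) |
| Nominal, clock started at the pre-dose Week 8 draw | Day 56 | Day 84 | Day 83 (84) | 0 (1) |

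The last row is for completeness. That subject is above 3x ULN at the end of Period 2 and should already be withdrawn under the Period 2 rule.

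**Counting convention.** If both end days are counted, Day 57 to Day 84 is 28 calendar days and the condition is met one day sooner. This adds at most one dose to any row. In the first row the condition would then be met on the morning drug is returned, so 0 doses are avoided, or 1 if a dose is taken that evening.

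**The case against.** The strongest reply accepts the calendar and disputes the consequence. Several parts of it stand.

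**No extra exposure is shown.** In Periods 1 and 2 the same row also keeps the subject on drug during monitoring and acts only when the period ends. An isolated elevation can therefore be dosed through for up to about 4 weeks in any period. In Period 3 the scheduled end of treatment has much the same effect on dosing as the end-of-period rule has earlier. A reader might infer that subjects at 200 mg are dosed longer on a raised ALT than the protocol accepts elsewhere. The documents do not show that.

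**Other protections remain.** A reader might also infer that no liver stopping rule works in Period 3. That is not so. Table 2 still discontinues drug at ALT or AST ≥5x ULN, and at ALT ≥3x ULN with raised bilirubin, raised INR or symptoms. It holds drug at ALT ≥3x ULN with raised bile acids. The dose-limiting toxicity rule (Section 6.1.1) and the Investigator's and Sponsor's discretion to stop (Section 6.1) also apply. Section 7.2.8 lets significant liver changes that fall short of the stopping rules be reported as adverse events of special interest. Drug-related ones prompt an ad hoc Safety Review Committee meeting (Section 7.2.9), and three or more on active drug stop the study (Section 6.1.9).

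**The stated risk is low.** Section 6.1.2 says hepatic toxicity is not reasonably expected at ≤200 mg QD and calls the table precautionary. The clinical elevations in Section 1.3 were at 400 and 1000 mg QD. This bears on how often the item would be needed, not on whether it can work as written.

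**Sparse testing is a separate matter.** After the first 200 mg dose, liver chemistry is next scheduled at Week 12, and the Week 10 contact is by telephone. Section 1.2.1 gives this as a deliberate design: "Safety visits are planned every 4 weeks at the end of each treatment period at a dose level". It is not a contradiction and adds no weight here, since the item would not act even with an unscheduled draw on Day 57.

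**Absolute zero is too strong.** The visit windows leave a sliver of room, as the working shows.

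**Conclusion.** The point holds for one item of Table 2. On the nominal schedule, the Period 3 condition for isolated ALT >3x ULN cannot be met before the last dose by an elevation that arises on 200 mg. The earliest day it can be met is Day 85, against a last dose on Day 83 or 84. Counting 28 elapsed days, at most 1 or 2 doses could be avoided, and only with both visit windows at their extremes and an unscheduled draw the morning after the first 200 mg dose. In practice the item is inoperative during dosing.

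This rests on evening dosing and morning draws, on 200 mg starting the evening of the Week 8 visit, on drug being returned at Week 12, and on the Period 2 withdrawal rule being applied to the Week 8 result. It is an internal inconsistency in a safety table with other safeguards around it. It does not show that liver safety is unprotected at the highest dose, and no efficacy analysis depends on it.

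**What to change.** The sponsor should reconcile three statements in the protocol: the Period 3 persistence condition in Table 2, the 4-week length of Period 3, and the end-of-period rule for Periods 1 and 2. Afterwards the item should either be able to operate during dosing or no longer be presented as a stopping criterion. Which clinical rule to adopt is for the clinical team, and none is proposed here.

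The cost is a short protocol clarification, with no effect on sample size or analysis. SAP Section 15 records that the study was discontinued early for business reasons. If the protocol is not revised again, the study report should describe accurately what this item could and could not do, and the wording should not be carried unchanged into a later protocol.

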6.1.3. QT Stopping Criteria

Study drug will be discontinued for a subject if either of the following criteria is met:

- QTcF >500 msec OR uncorrected QT >600 msec
- Change from Screening in QTcF of >60 msec

One repeat ECG should be performed to confirm the accuracy and persistence of an initial result that fulfills the QT stopping criteria.

6.1.4. Suicidality Stopping Criteria

Tildacerfont is considered to be a central nervous system (CNS)-active drug. Some CNS-active drugs may be associated with an increased risk of suicidal ideation in certain populations. Although tildacerfont has not been shown to be associated with an increased risk of suicidal ideation or behavior in past clinical studies, subjects will be monitored for such events during this study using the C-SSRS.

Individuals who answer “yes” to Question 3, 4, or 5 in the suicidal ideation section of the C-SSRS at screening or baseline are not eligible for this study. Any subject who exhibits any Suicidal Behavior or Suicidal Ideation (eg, answers “yes” to Question 3, 4, or 5 in the suicidal ideation section of the C-SSRS) will have study drug immediately discontinued and should be evaluated by a psychiatrist. This safety finding will be considered an AESI if it is not an SAE (eg, requiring hospitalization) (see [Section 7.2.8](#)).

6.1.5. Depression or Anxiety Stopping Criteria

Any subject who develops severe depression or anxiety CTCAE Grade 3 or higher, as assessed by the Investigator, will require study drug discontinuation and appropriate follow-up. This will be considered an AESI if it is not an SAE (eg, requiring hospitalization) (see [Section 7.2.8](#)).

6.1.6. Adrenal Insufficiency Stopping Criteria

Symptoms of adrenal insufficiency include weakness, tiredness, anorexia, nausea, vomiting, abdominal pain, orthostasis and muscle and joint aches. Weight loss and hypotension (eg, systolic blood pressure <110 mmHg) are also associated with adrenal insufficiency. Hyponatremia, hyperkalemia, hypercalcemia, azotemia, anemia, and eosinophilia may accompany adrenal insufficiency. It is important to note that many of these signs, symptoms and laboratory findings are nonspecific and commonly occur in persons without adrenal

insufficiency. The Investigator should use their clinical judgment when determining whether the signs, symptoms or laboratory findings are isolated AEs or are possibly due to adrenal insufficiency.

The Investigator is strongly encouraged to contact the medical monitor to review the presentation and discuss the plan for subjects with any AEs of adrenal insufficiency or cortisol measurements below the normal range.

If a subject develops clinical and/or laboratory findings of adrenal insufficiency that are confirmed with serum cortisol measurement, the AE of "adrenal insufficiency" should be reported on the AE/SAE CRF. The sign(s), symptom(s) and laboratory findings resulting in the diagnosis of adrenal insufficiency will be collected on separate Adrenal Insufficiency CRF and should not be individually recorded on the AE CRF. If the serum cortisol level is within the normal range, the individual symptoms and/or other laboratory findings should be reported as individual AEs.

In the absence of clinical or laboratory findings of adrenal insufficiency, unconfirmed serum cortisol levels below the normal range should not be reported as AE. Confirmed by repeat serum cortisol levels below the normal range, even in the absence of clinical or laboratory findings of adrenal insufficiency, are to be reported as an AE of adrenal insufficiency.

If at a telephone visit or at an unscheduled contact, the subject reports symptoms compatible with adrenal insufficiency, dosing with study drug should be suspended. The subject should report to the clinic the next morning at 8 A.M. for serum cortisol measurement. The sample should be sent to the clinic's local laboratory for an expedited measurement. A second sample should be sent to the central laboratory for centralized measurement. The Investigator should use the results from the local laboratory to determine if dosing may be resumed (normal serum cortisol measurement) or permanently discontinued.

If at a routinely scheduled clinic visit, the subject reports symptoms compatible with adrenal insufficiency, dosing with study drug should be suspended. A serum sample should be drawn and sent to the clinic's local laboratory for an expedited cortisol measurement. The Investigator should use the results from the local laboratory to determine if dosing may be resumed (normal serum cortisol measurement) or permanently discontinued. The serum cortisol measurement scheduled to be done by the central laboratory should be performed as scheduled.

If the serum cortisol level from a routinely scheduled clinic visit is below the normal range but the subject did not at the clinic visit report adverse events possibly related to adrenal insufficiency, the site should contact the subject, collect spontaneously reported AEs since the clinic visit and have the subject return to the clinic as soon as possible for a repeat 8 A.M. serum cortisol measurement done by the central laboratory. If the subject does not report symptoms of adrenal insufficiency and at the discretion of the Investigator, study drug may be continued until the serum cortisol measurement by the central laboratory is available.

Alternatively, if the Investigator believes that the subject may have symptoms consistent with adrenal insufficiency, the study drug should be held and a serum sample sent to the clinic's local laboratory for an expedited cortisol measurement. If the repeat serum cortisol level is

below the normal range either done by the central or local laboratory, study drug should be permanently discontinued, and the Early Termination Visit be conducted.

If a subject develops an AE of adrenal insufficiency meeting the seriousness criteria as defined in [Section 7.2.2](#) or the event is severe in nature and in addition to suspending administration of study medication, the Investigator may consider treatment with glucocorticoid therapy. The route, type and dose of glucocorticoid treatment as well as the duration of therapy are at the discretion of the Investigator and should be in accordance with the local treatment guidelines for the treatment of adrenal insufficiency.

If a subject develops an adrenal insufficiency AE meeting the seriousness criteria as defined in [Section 7.2.2](#) or the event is severe in nature, regardless of the outcome of the serum cortisol measurement, study drug should be permanently discontinued, and the subject should undergo the Early Termination Visit.

All serious or non-serious AEs of adrenal insufficiency are considered AESI.

